1. AMENDMENT HISTORY

Amendment No.	Protocol Version No.	Date issued	Author(s) of changes	Details of Changes made

2. SYNOPSIS

Study Title	THE ASSESSMENT OF CEREBRAL HAEMODYNAMICS IN PATIENTS WITH TRANSIENT ISCHAEMIC ATTACK: A TRANSCRANIAL DOPPLER STUDY
Internal ref. no.	UNOLE 0694
Trial Design	Single-centre, prospective, case control study
Trial Participants	Participants with Transient Ischaemic Attack (TIA) and healthy adults (HC)
Planned Sample Size	40 participants in total; 20 participants with TIA and 20 HC
Follow-up duration	N/A
Planned Trial Period	6 months
Primary Objective	To determine the beat-to-beat cerebral blood flow velocity (CBFv) of both TIA and HC subjects during performance of a squat-stand manoeuvre
Secondary Objective	To determine other beat-to-beat cerebral haemodynamic parameters, specifically autoregulation index (ARI), of both TIA and HC subjects during performance of a squat-stand manoeuvre
Outcome Measures	
This is not an intervention study, and therefore it would not be appropriate to assess classical primary and secondary outcome measures such as death and disability for this study. However, we intend to evaluate the following relevant outcomes:
 
 1. The number of participants successfully recruited 2. The number of recruited participants able to comply with the full measurement protocol. 3. The number of measurements rejected because of aspects related to data quality during the analysis protocol, with recorded reasons. 4. Overall, the number of recruited subjects in whom values for the following parameters can be derived: 
 • % change of cerebral blood flow velocity (CBFv) at baseline in response to performance of a squat-stand manoeuvre • Autoregulation index

3. ABBREVIATIONS

AE	Adverse event
AR	Adverse reaction
ARI	Autoregulation Index
BP	Arterial Blood Pressure
CA	Cerebral Autoregulation
CBF	Cerebral Blood Flow
CBFv	Cerebral Blood Flow Velocity
CHIASM	Cerebral Haemodynamics in Ageing and Stroke Medicine
CI	Chief Investigator
CPP	Cerebral Perfusion Pressure
CrCP	Critical Closing Pressure
CRF	Case Report Form
CT	Computerised Tomography
dCA	Dynamic Cerebral Autoregulation
ECG	Electrocardiogram
EtCO ₂	End-Tidal Partial Pressure of Carbon Dioxide
fMRI	Functional Magnetic Resonance Imaging
GCP	Good Clinical Practice
HC	Healthy Control
HR	Heart Rate
ICH	International Conference on Harmonisation of Technical Requirements for Registration of Pharmaceuticals for Human Use
ISF	Investigator Site File
LRI	Leicester Royal Infirmary
MCA	Middle Cerebral Artery
PET	Positron Emission Tomography
PIL/S	Participant Information Leaflet/Sheet
RAP	Resistance Area Product
SAE	Serious Adverse Event
SAR	Serious Adverse Reaction
SCA	Static Cerebral Autoregulation
SSM	Squat stand manoeuvre
SOP	Standard Operating Procedure
SPECT	Single photon emission computed tomography
SUSAR	Suspected Unexpected Serious Adverse Reactions
TCD	Transcranial Doppler Ultrasound
TFA	Transfer Function Analysis
TIA	Transient Ischaemic Attack
TMF	Trial Master File
UK	United Kingdom

4. BACKGROUND AND RATIONALE

Adequate cerebral blood flow (CBF) is essential for brain survival and function. Brain metabolism is almost entirely dependent on oxidative mechanisms, particularly the metabolism of glucose, and the brain has a very limited capacity for anaerobic function. Adequacy and constancy of cerebral blood flow are therefore vital in ensuring both a steady supply of oxygen, glucose and other nutrients, and the removal of waste products of metabolism.

Cerebral autoregulation (CA) refers to the ability of the brain to maintain a relatively constant CBF in response to significant changes in cerebral perfusion pressure (CPP). Thus, in response to an increase or decrease in CPP, there is a vasodilatation or vasoconstriction of cerebral vessels. This variable resistance to flow occurs mainly in the cerebral arteriolar bed; the major cerebral arteries are essentially conductive rather than compliant [Itoh et al 2012, Kuga et al 2009, Kontos et al 1978]. The classic concept of CA whereby, under normal physiological conditions, CBF is around 50ml/100g/min, and this is maintained across a wide range of blood pressures (MAP of 60-160mmHg), was first described by Lassen in 1959. CA is usually described as being static (sCA), reflecting the integrity of such mechanisms over time, or dynamic (dCA), occurring in response to sudden fluctuations in perfusion pressure. CA is accomplished through the complex interplay of a variety of myogenic, metabolic and neurogenic mechanisms.

In recent years, there has been growing evidence that CA is altered in various disease states including ischaemic stroke [Eames et al 2002], head injury [Czosynka et al 1996], carotid stenosis [Reinhard et al 2004], pre-eclampsia [van Veen et al 2013], chronic diabetes mellitus [Chiu et al 2005], Alzheimer's dementia [Claassen et al 2011], and idiopathic Parkinson's disease [Haunton 2013].

In ischaemic stroke, impaired CA is related to neurological deterioration, the necessity for decompressive surgery, and poor prognosis [Aries et al 2010]. CA has also been shown to correlate with stroke severity and functional outcomes [Llwyd et al 2018].

Transient ischaemic attack (TIA) is defined as "a transient episode of neurologic dysfunction caused by focal brain, spinal cord or retinal ischemia without acute infarction" [Easton et al 2009]. Approximately 46,000 people in the UK each year have a first TIA [Rothwell et al 2005] and one in 12 people will have a full stroke within a week of having a TIA [Coull et al 2004]. Urgent assessment in a specialist TIA clinic ensures timely and appropriate investigations and rapid interventions (such as antiplatelet therapy, blood pressure-lowering medication, statins, anticoagulation and carotid

endarterectomy or stenting where appropriate) [Rothwell et al 2007]. TIA and acute ischaemic stroke share the same pathophysiological mechanisms and, whilst there have been a significant number of studies investigating cerebral haemodynamics and CA in acute stroke, there have been very few studies exploring CA and TIA. A study by Atkins et al reported no impairment of cerebrovascular haemodynamic control following TIA [Atkins et al 2010]. However, recent abstract level data suggest altered CA is predictive of patients who go on to have further TIAs and strokes [Musthak et al 2017].

Cerebral haemodynamics can be studied using techniques such as functional magnetic resonance imaging (fMRI), positron emission tomography (PET) or single-photon emission computed tomography (SPECT). However, these techniques are expensive, in the case of SPECT involve radiation, and there are feasibility issues including the need to lie still for prolonged periods and to have no metal implants. Transcranial Doppler Ultrasonography (TCD) is a simple, non-invasive imaging modality with high temporal resolution which allows for continuous and bilateral recording of cerebral blood flow velocity (CBFv) through the major cerebral arteries [Aaslid et al, 1982]. TCD has the advantage that CBFv measurements can be made in standing, seated, tilted and supine positions. Continuous measurements of CBFv using TCD have shown that CBFv is affected by perturbations in arterial blood pressure (BP) [Aaslid et al 1989].

The most widely used, validated, modelling technique in the analysis of the relationship between CBFv and BP is transfer function analysis (TFA) [Claassen et al 2016]. TFA makes it possible to examine the effect of changes in (BP) on CBFv. It quantifies the extent to which the input signal, BP, is reflected in the output signal, CBFv, and was first proposed by Giller.

Cerebral haemodynamic data which can be obtained using TFA include values of coherence, phase, gain, autoregulatory index (ARI), critical closing pressure (CrCP) and resistance area product (RAP). The ARI was derived in 1995 by Tiecks et al using of equations and curves based on the CBFv response to a sudden fall in induced by thigh cuff deflation. These equations and curves allow for the calculation of an ARI value from 0 to 9, where 0 represents absence of autoregulation i.e. CBF dependent on CPP, (a 'pressure-passive relationship') and 9 represents best measurable autoregulation. 'Normal' autoregulation is represented by an ARI of 5 ± 1 .

Whilst CA can be evaluated using spontaneous fluctuations in BP [Brodie et al 2009], coherence between oscillations at these low frequencies ($<0.07\text{Hz}$) is generally low (0.5), which often leads to the exclusion of such data from analysis in studies of CA [Claassen et al 2016]. Furthermore, larger and induced perturbations of BP allow us to study the CBF response to BP with increased certainty that there is a causal relationship. Larger magnitude BP changes can be induced using challenges

such as bilateral thigh cuff inflation to suprasystolic blood pressure and their simultaneous release, lower body negative pressure, and the cold pressor stimulus (placing a hand in ice water). These can be uncomfortable for participants. More recently, squat-stand manoeuvres (SSMs) have also been shown to produce large changes in BP and thus CBFv [Claassen et al 2009a, Smirl et al 2015, Barnes et al 2017]. Squatting induces a rapid but transient rise in BP with its peak after approximately 2-3 seconds (s). This increase in BP has been attributed to a sudden increase in cardiac output from increased venous return from the lower limbs. The subsequent reduction in BP on standing up has been attributed to a combination of reduction in peripheral vascular resistance and a reduction in cardiac output due to rapid return of central blood volume to the lower limbs [Smirl et al 2015]. SSMs can be more comfortable for participants and are arguably more representative of physiological BP challenges in daily life, e.g. bending down to pick something up from the floor and standing up after tying a shoelace, than those other BP challenges detailed above. When SSMs are performed repeatedly, large and periodic changes in BP and CBFv are created. SSMs have been shown to be safe and well tolerated in various populations including heart transplant recipients [Smirl et al 2014], young and old healthy controls [Oudegeest-Sander et al 2014, Barnes et al 2017], and patients with Alzheimer's dementia [Claassen JA et al 2009b]. It has recently been shown that reliable CA data can be obtained from as few as three SSMs [Barnes et al 2018].

The proposed study will investigate and compare the beat-to-beat CBFv changes observed during performance of a SSM protocol in 20 participants with acute (within 7 days) TIA and 20 HC. The proposed study will also investigate whether performance of a SSM is associated with differences in other beat-to-beat cerebral haemodynamic parameters, specifically autoregulation index (ARI), between participants with acute (within 7 days) TIA and 20 HC. In doing so, it is hoped that we will be able to establish if CA is impaired in patients with TIA.

5. OBJECTIVES

5.1 Primary Objective

To determine the beat-to-beat cerebral blood flow velocity (CBFv) of both TIA and HC subjects during performance of a SSM.

5.2 Secondary Objective

To determine other beat-to-beat cerebral haemodynamic parameters, specifically autoregulation index (ARI), of both TIA and HC subjects during performance of a SSM.

6. STUDY DESIGN

6.1 Summary of Trial Design

This is a single-centre, prospective, case control study which will run for six months. 20 patients with acute TIA (within 7 days), and 20 healthy controls will be recruited from the specialist TIA clinic at University Hospitals of Leicester NHS Trust. Participants will be eligible if they are aged over 18 and can consent to participate. They won't be able to participate if they have severe heart failure, an irregular heartbeat, blocked neck blood vessels, severe breathing problems, if they do not understand written or verbal English, if they have inadequate ultrasound windows, or if they are pregnant.

TIA participants will be given a minimum of 1 hour, and a maximum of 48 hours to decide whether or not to take part in the study, but must undertake the study assessment within 7 days of their TIA. Healthy control participants will be given a minimum of 1 hour, and a maximum of 7 days to decide whether or not to take part in the study. There is no time restriction on when they undertake the study assessment.

All participants will undergo an assessment of brain blood flow using TCD, during which their heart rate, breathing and blood pressure will also be monitored. During the assessment participants will sit quietly before being asked to stand and then complete a squat-stand manoeuvre in time with a computer sequence. The research visit will take approximately 90 minutes, the TCD assessment itself will take approximately 1 hour and participants only need to attend once.

6.2 Primary and Secondary Endpoints/Outcome Measures

This is not an intervention study, and therefore it would not be appropriate to assess classical primary and secondary outcome measures such as death and disability for this study. However, we intend to evaluate the following relevant outcomes:

- a) The number of participants recruited
- b) The number of participants able to comply with the full measurement protocol
- c) The number of measurements rejected because of aspects related to data quality during the analysis protocol, with recorded reasons
- d) Overall, the number of recruited subjects in whom values for the following parameters can be derived:
 - % change of cerebral blood flow velocity (CBFv) at baseline in response to performance of a squat-stand manoeuvre
 - Autoregulation index

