11. STATISTICS

11.1 Statistical analysis

The null hypotheses being tested are:

- cerebral haemodynamic parameters, including CBFv and ARI, do not differ between baseline recordings and during performance of squat-stand manoeuvres
- cerebral haemodynamic parameters, including CBFv and ARI, do not differ between TIA patients and HC

All data will be tested for normality prior to statistical testing using Shapiro-Wilks. Categorical data will be reported as absolute number and percentages. Continuous data will be plotted and assessed for normality; normally distributed continuous variables will be described as mean (SD) and continuous variables with skewness as median (IQR). Statistical testing for differences between HC and TIA groups will be by two-way ANOVA for continuous, parametric data, Friedman 2 way analysis of variance for continuous, non-parametric data, and Chi-Square for nominal data.

Data will be recorded in Microsoft Excel. Statistical analyses will be performed using the latest versions of SPSS for Windows or Statistica, and graphs will be produced using the latest version of Statistica.

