11.2 Sample size calculation

A formal sample size calculation was not possible for this study therefore a realistic number of participants has been selected based on previous experience of similar research studies by [name], [name] and [name].

Brodie FG et al reported in 2009 that a sample of 11 patients per group will allow the detection of a difference in ARI of 2 units between groups, with 80% power at the 5% significance level.

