11.3 The Level of Statistical Significance

Statistical significance will be set at $p < 0.05$

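### Every listed outcome is a count, while the plan tests an open list of parameters for TIA versus healthy controls at p < 0.05 with no primary contrast

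*Combined protocol and SAP*

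**What the plan says.** - **Outcomes (6.2, repeated in the synopsis).** Items (a) to (c) count participants recruited, participants who complete the protocol, and measurements rejected. Item (d) is "Overall, the number of recruited subjects in whom values for the following parameters can be derived", followed by % change in CBFv and ARI. The section declines a conventional hierarchy because "it would not be appropriate to assess classical primary and secondary outcome measures such as death and disability for this study".
- **Objectives.** Primary (5.1): "To determine the beat-to-beat cerebral blood flow velocity (CBFv) of both TIA and HC subjects during performance of a SSM". Secondary (5.2): "To determine other beat-to-beat cerebral haemodynamic parameters, specifically autoregulation index (ARI), of both TIA and HC subjects during performance of a SSM". Neither states a contrast between groups.
- **Aim (4).** The study is to compare the two groups, and "it is hoped that we will be able to establish if CA is impaired in patients with TIA".
- **Hypotheses (11.1).** There are two nulls. One is that parameters do not change from baseline to the squat-stand manoeuvre (SSM). The other is that "cerebral haemodynamic parameters, including CBFv and ARI, do not differ between TIA patients and HC". Group differences are tested by two-way ANOVA, or by non-parametric or chi-square alternatives, with no model term singled out.
- **Sample size (11.2).** No formal calculation was possible. The section then cites an earlier study in which "a sample of 11 patients per group will allow the detection of a difference in ARI of 2 units between groups".
- **Significance (11.3).** "Statistical significance will be set at" p < 0.05, with no restriction to a primary test and no multiplicity rule.

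**The concern.** Sections that should point to the same result do not. The endpoints section measures feasibility, whereas the background, objectives and statistics sections describe a physiological comparison of TIA with HC. A report could deliver every item in 6.2 and leave open whether CA is impaired after TIA.

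The comparison is planned in 11.1, but as an open list of parameters judged at the same threshold. Since none is designated as the main group contrast, whichever falls below 0.05 can be presented as the answer once the data are known, and a reader cannot tell how many others were tried.

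**Working it through.** **The plan's own figure.** Section 11.2 cites 11 per group for 2 ARI units, 80% power and a 5% level. No SD is given, so the figure cannot be reproduced from the document. The SD it implies (two-sided, normal approximation) is 2 / [(1.960 + 0.842) × √(2/11)] = 1.67; the t-based value is 1.59. The planned 20 per group exceeds the cited 11. The figure matters here only because the sole power statement concerns the secondary parameter.

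**Does any listed outcome carry the comparison?**

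| Item in 6.2 | What it yields | TIA versus HC contrast? |
|---|---|---|
| (a) recruited | count of people | no |
| (b) complied | count of people | no |
| (c) rejected | count of measurements | no |
| (d) derivable | count of people with a CBFv change or ARI value | no |

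**Which tests bear on the TIA question?** Only the second null in 11.1. Rejecting the first shows that squatting changes a parameter, and section 4 already says that SSMs produce large changes in blood pressure (BP) and hence CBFv.

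**Chance of at least one false positive among the group comparisons.** Each test is at 0.05 and all group nulls are taken as true. With k independent tests the chance is 1 − 0.95^k; under any dependence it is at most k × 0.05.

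- One named test: 5%.
- k = 2 (CBFv and ARI, the two named in 11.1): 1 − 0.95² = 9.75%; bound 2 × 0.05 = 10%.
- k = 7 (CBFv plus the six that section 4 lists: coherence, phase, gain, ARI, critical closing pressure, resistance area product): 1 − 0.95⁷ = 30.2%; bound 7 × 0.05 = 35%.

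The plan never fixes k. Two is the minimum from the text; seven is an assumption. Positive correlation between parameters would lower the 30.2%.

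**Would naming CBFv alone give one test?** Not yet.

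- **Baseline.** Item (d) does not say which one. Section 8.5 offers a seated recording, a quiet standing recording, and 90-second standing periods at each end of the SSM recording.
- **Two arteries.** Both middle cerebral arteries (MCAs) are recorded, with no rule for combining them.
- **Model term.** The ANOVA is tied neither to a group effect nor to a group-by-manoeuvre interaction.

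**Would a CBFv difference show impaired CA?** Not by itself. CBFv change also depends on the BP change, and section 8.5 lets participants choose their own squat depth. Section 4 presents ARI as the graded measure of autoregulation.

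**The case against.** The best defence is that this is a 40-person, non-interventional study for which counts are sensible outcomes, that objectives 5.1 and 5.2 already rank CBFv above ARI, and that the group comparison is stated in sections 4 and 11.1. Much of this stands. The ranking is real, and the comparison is missing only from the endpoints section. Treating all secondary results as exploratory is also one acceptable convention among several.

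It does not dispose of the point. The protocol sets null hypotheses, tests and a significance level, so it is not purely a feasibility study. Ruling out death and disability as outcomes is no reason to omit a physiological endpoint. Ranking CBFv as an objective supplies no contrast, baseline or test.

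Three stronger readings are tempting, and the documents do not support them:

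- **Three rival main results.** A reader might infer that CBFv, ARI and the counts compete equally. But 5.1 and 5.2 rank the first two, and 11.2 offers the ARI figure as a precedent after saying no formal calculation was possible. It does not nominate ARI.
- **An error rate of 18.5% or 33.7%.** These come from 1 − 0.95⁴ and 1 − 0.95⁸. The first can be reached by counting baseline-versus-SSM tests, which do not bear on TIA and whose null is expected to be false for CBFv. The second also assumes separate, independent tests in each hemisphere. Nothing says the hemispheres are tested separately, and independence is implausible for two arteries in one person under the same BP.
- **A sample size error.** Nothing here shows one.

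**Conclusion.** The point holds as a mismatch between endpoints and aim: no endpoint in 6.2 or the synopsis carries the TIA versus HC comparison, and no group contrast is primary. For the question about TIA, the false-positive chance is 9.75% for the two named parameters if independent and at most 10% otherwise. It is about 30% if all seven named parameters are tested independently. The lower figure rests on the text of 11.1; the upper rests on an assumed number of tests and would fall with correlation. The study remains feasible, but its main inference is not fixed in advance. The change should be made before any data are seen.

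**What to change.** 1. **Primary endpoint (6.2 and synopsis).** The TIA minus HC difference in % change of CBFv from baseline to SSM, in line with 5.1. State one baseline (for example the 90-second standing period that opens recording 3) and one rule for the two MCAs (for example their mean), so that this is one test.
2. **Single secondary endpoint.** The TIA minus HC difference in ARI during the SSM. Base any statement that CA is impaired on ARI. If the sponsor wants the CA question to be the main test, name ARI as primary instead, before data are seen.
3. **Feasibility outcomes.** List the four counts separately. Use consented participants as the denominator for (b) and (d), since 8.3 checks the ultrasound windows after consent and cites inadequacy rates of 5–37%. Use measurements attempted as the denominator for (c).
4. **Sections 11.1 and 11.3.** Apply p < 0.05 as confirmatory to the one primary group comparison only. Report the remaining comparisons as estimates with 95% CIs, labelled exploratory.

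**Cost.** Protocol wording only; no extra data, visits or participants. The downside is that secondary p-values below 0.05 can no longer be presented as confirmatory. With CBFv as primary, a conclusion about CA drawn from ARI would therefore be exploratory, and the precedent in 11.2 would not support the main test. For CBFv, 20 analysable participants per group give 80% power for a difference of about 0.91 SD (two-sided t-test). The documents give no CBFv SD with which to express this as a % change.
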